5 METHODOLOGY

5.1 Entry Criteria

5.1.1 *Diagnosis/Condition for Entry into the Trial*

The study will be conducted in male subjects with histologically confirmed mCRPC who have progressed or become resistant to no more than 2 prior systemic treatment regimens with chemotherapy, targeted therapies, radiopharmaceuticals, or immunotherapy in the metastatic setting. Hormonal treatment will not be considered when determining the number of prior regimens in the metastatic setting. Subjects cannot have had more than 1 prior chemotherapeutic regimen in the metastatic setting. Subjects with evidence of progressive bone or other metastases are acceptable. Subjects may remain on castration therapy (luteinizing-hormone-releasing hormone [LHRH] agonist or antagonist) during the trial.

5.1.2 *Subject Inclusion Criteria*

In order to be eligible for participation in this trial, the subject must:

1. Be willing and able to provide written informed consent for the trial.
2. Be ≥ 18 years of age on day of signing informed consent.
3. Have progressive metastatic castration resistant prostate cancer, on androgen deprivation therapy, based on at least one of the following criteria:
 - a. PSA progression defined as 25% increase over baseline value with an increase in the absolute value of at least 2 ng/mL that is confirmed by another PSA level with a minimum of a 1-week interval with a minimum PSA of 2 ng/ml.
 - b. Progression of bi-dimensionally measurable soft tissue (nodal metastasis) assessed within 1 month prior to registration by a CT scan or MRI of the abdomen and pelvis (please refer to [Section 7.1.2.5.1](#) for definitions of measurable disease).

- c. Progression of bone disease (evaluable disease) (new bone lesion(s)) by bone scan. (Please refer to [Section 7.1.2.5.1](#) for definitions of evaluable disease).
4. Has discontinued antiandrogens (bicalutamide, nilutamide) >6 weeks and enzalutamide or abiraterone >4 weeks prior to Day 1 of trial treatment
5. Have a performance status of 0 or 1 on the ECOG Performance Scale.
6. Demonstrate adequate organ function as defined in [Table 3](#). All screening labs should be performed within 28 days of treatment initiation.

Table 3 Adequate Organ Function Laboratory Values

System	Laboratory Value
Hematologic	
Absolute neutrophil count (ANC) ^a	≥1000 /mcL
Platelets ^a	≥75,000 / mcL
Hemoglobin ^a	≥9 g/dL or ≥5.6 mmol/L
Lymphocytes	≥500 / mcL
Renal	
Serum creatinine OR Measured or calculated ^b creatinine clearance (CrCl) (GFR can also be used in place of creatinine or CrCl)	≤1.5 X upper limit of normal (ULN) OR ≥50 mL/min for subject with creatinine levels > 1.5 X institutional ULN
Hepatic	
Serum total bilirubin	≤ 1.5 X ULN OR Direct bilirubin ≤ ULN for subjects with total bilirubin levels > 1.5 ULN
AST (SGOT) and ALT (SGPT)	≤2.5 X ULN OR ≤5 X ULN if liver metastases are present
Coagulation	
International Normalized Ratio (INR) or Prothrombin Time (PT)	≤1.5 X ULN unless subject is receiving anticoagulant therapy as long as PT or INR is within therapeutic range of intended use of anticoagulants
Activated Partial Thromboplastin Time (aPTT)	≤1.5 X ULN unless subject is receiving anticoagulant therapy as long as aPTT is within therapeutic range of intended use of anticoagulants

^a ANC, Platelets and Hemoglobin requirements cannot be met by use of recent transfusion or growth factor support (G-CSF, erythropoietin, etc) within 2 weeks prior to treatment initiation

^b Creatinine clearance should be calculated per institutional standard.

7. Male subjects should agree to use an adequate method of contraception starting with the first dose of study therapy through 120 days (approximately 4 months) after the last dose of study therapy.

5.1.3 *Subject Exclusion Criteria*

The subject must be excluded from participating in the trial if the subject:

1. Received more than 2 prior systemic treatment regimens with chemotherapy, targeted therapy, radiopharmaceuticals, or immunotherapy in the metastatic setting or received more than 1 prior chemotherapeutic regimen in the metastatic setting.
2. Is currently participating and receiving study therapy or has participated in a study of an investigational agent and received study therapy or used an investigational device within 4 weeks of the first dose of treatment.
3. Has a diagnosis of immunodeficiency or is receiving any systemic steroid therapy, abiraterone acetate, other androgen synthesis inhibitors or any form of immunosuppressive therapy within 7 days prior to Day 1 of trial treatment. The use of physiologic doses of corticosteroids may be approved after consultation with the Sponsor.
4. Has had a prior monoclonal antibody or autologous cellular immunotherapy within 4 weeks prior to study Day 1 or who has not recovered (i.e., \leq Grade 1 or at baseline) from AEs due to agents administered more than 4 weeks earlier.
 - Note: Subjects currently receiving denosumab are an exception and may qualify, however introduction of denosumab is not allowed while on study.
5. Has had prior chemotherapy, targeted small molecule therapy, or radiation therapy within 2 weeks prior to study Day 1 or who has not recovered (i.e., \leq Grade 1 or at baseline) from AEs due to a previously administered agent.
 - Note: Subjects with \leq Grade 2 neuropathy are an exception to this criterion and may qualify for the study with Sponsor approval.
6. Has a known additional malignancy that is progressing or requires active treatment. Exceptions include basal cell carcinoma of the skin; squamous cell carcinoma of the skin or superficial urothelial cancer 2 years post therapy.
7. Has known active central nervous system (CNS) metastases and/or carcinomatous meningitis. Subjects with previously treated brain metastases may participate provided they are stable (without evidence of progression by imaging for at least 4 weeks prior to the first dose of trial treatment and any neurologic symptoms have returned to baseline), have no evidence of new or enlarging brain metastases, and are not using steroids for at least 7 days prior to trial treatment. This exception does not include carcinomatous meningitis which is excluded regardless of clinical stability.

8. Has an active autoimmune disease requiring systemic treatment within the past 3 months (i.e., with use of disease modifying agents, corticosteroids or immunosuppressive drugs). Replacement therapy (e.g., thyroxine, insulin or physiologic corticosteroid replacement therapy for adrenal or pituitary insufficiency, etc.) is not considered a form of systemic treatment.
 - Note: Subjects with vitiligo or resolved childhood asthma/atopy may be allowed with Sponsor approval.
 - Note: Subjects who require intermittent use of inhaled steroids, bronchodilators or local steroid injections may be allowed with Sponsor approval.
 - Note: Subjects with hypothyroidism stable on hormone replacement or Sjogrens syndrome may be allowed with Sponsor approval.
9. Has evidence of interstitial lung disease or current pneumonitis or a history of (non-infectious) pneumonitis that required steroids.
10. Has an active infection requiring systemic therapy. Prior to dosing with ADXS31-142, the subject must be at least 5 half-lives from their last dose of antibiotic.
11. Has a history of listeriosis or current evidence of any condition, therapy, or laboratory abnormality that might confound the results of the trial, interfere with the subject's participation for the full duration of the trial, or is not in the best interest of the subject to participate, in the opinion of the treating investigator.
12. Has known psychiatric or substance abuse disorders that would interfere with cooperation with the requirements of the trial.
13. Has received prior therapy with an anti-PD-1, anti-PD-L1, or anti-PD-L2 agent or if the subject has previously participated in a Merck MK-3475 clinical trial. (Not applicable in enrollment to Part A)
14. Has a history of human immunodeficiency virus (HIV) (HIV 1/2 antibodies).
15. Has a history of hepatitis B or hepatitis C.
16. Has received a live vaccine within 30 days prior to Day 1 of trial treatment.
17. Has implanted medical device(s) that pose a high risk for colonization and/or cannot be easily removed (e.g., prosthetic joints, artificial heart valves, pacemakers, orthopedic screw(s), metal plate(s), bone graft(s), or other exogenous implant(s)). NOTE: More common devices and prosthetics which include arterial and venous stents, dental and breast implants and venous access devices (e.g., Port-a-Cath or Mediport) are permitted. Sponsor must be contacted prior to consenting any subject who has any other device and/or implant.

18. Patients who are currently receiving or who have received any PI3K within 30 days prior to registration.
19. Any currently requiring or anticipated to require TNF blocking agent (e.g., infliximab) therapy for diagnosis of rheumatologic disease or inflammatory bowel disease (e.g., ankylosing spondylitis, Crohn disease, plaque psoriasis, psoriatic arthritis, rheumatoid arthritis, or ulcerative colitis) during study therapy administration and within 30 days of the last dose of study therapy.
20. Has a contraindication to administration of trimethoprim/sulfamethoxazole and ampicillin.
21. Has contraindication to administration of NSAIDS.
22. Has undergone major surgery within 6 weeks prior to the initiation of ADXS31-142 treatment. NOTE: All toxicities and/or complications must have recovered to baseline or Grade 1 prior to the initiation of ADXS31-142 study therapy. Sponsor must be contacted prior to enrolling subjects on the study who recently had major surgery or have new artificial implant, and/or devices.
23. Is or has an immediate family member (spouse or children) who is directly involved with this trial, that is employed by the investigational site or Sponsor, unless prospective Institutional Review Board (IRB) approval (by chair or designee) is given allowing exception to this criterion for a specific subject.
24. Has severe hypersensitivity (\geq Grade 3) to pembrolizumab and/or any of its excipients.

5.2 Trial Treatments

The treatments to be used in this trial are outlined below in [Table 4](#). Trial treatment should begin within 5 days of eligibility confirmation.

Table 4 Trial Treatments

Drug	Dose	Route of Administration	Regimen
ADXS31-142	0.5×10^9 , 1×10^9 , 5×10^9 , or 1×10^{10} cfu	IV infusion	Day 1 of Wks 1, 4 and 7, Q12W cycle
Pembrolizumab (MK-3475)	200 mg	IV infusion	Q3W

5.2.1 Dose Selection/Modification

The doses to be used in each part of the trial are described below.

5.2.1.1 Dose Selection

The rationale for the ADXS31-142 starting dose and the pembrolizumab (MK-3475) fixed dose are discussed in [Section 4.2.2](#). In Part A of the trial, the study was originally designed to include

dose-escalation/de-escalation with the decisions based on interim safety data review or pre-defined DLT criteria ([Section 5.2.1.1.1](#) – Dose Limiting Toxicity Criteria) and be based on 3 dosing intervals (below RP2D, at RP2D, or above RP2D) according to a mTPI with precalculated decisions that can easily be referred to ([Table 5](#)) [30, 31]. The TPI method would provide for exposure to fewer subjects to toxic doses above the MTD and yield similar probabilities in identifying the correct MTD, even when the sample size is matched [31]. A minimum of 3 subjects will be evaluated in each cohort before dose-escalation decisions are made. Table 5 consists of all the dose-escalation rules for the trial. If the toxicity rate of the currently used dose level is within the “under dosing” interval, the mTPI design recommended escalating the dose level; in the case of proper dosing, this design would recommend continuing at the current dose; for cases where toxicities indicate “over dosing”, the mTPI design would recommend de-escalating the dose level. As dosing was not determined based on this study alone, it was decided that escalation to 5×10^9 cfu or 1×10^{10} cfu would no longer be included in this study design. This is based on overall review of the safety data across the *Lm*-based program of clinical trials which determined that the starting dose would be 1×10^9 cfu. At the RP2D level in Part A up to 10 subjects may be enrolled. The Sponsor reserves the right to add additional subjects in order to further evaluate safety and tolerability. All decisions on dose-escalation and dose de-escalation will be made by the Sponsor only after discussions between Sponsor and Investigators have occurred.

Table 5 Dose Decisions for ADXS31-142 Monotherapy (Targeted DLT Rate = 25%)

The table is based on a sample size of 21 subjects. Two parameters epsilon1 and epsilon2 are set at default values [30] of 0.05. X-axis is number of subjects treated at current dose; y-axis is number of toxicities.

mTPI Decision Table

Sample Size = 21 ; Target Toxicity Probability = 0.25 ; epsilon 1 = 0.05 ; epsilon 2 = 0.05

ESCALATE STAY DE-ESCALATE UNACCEPTABLE

	1	2	3	4	5	6	7	8	9	10	11	12	13	14	15	16	17	18	19	20	21
0	E	E	E	E	E	E	E	E	E	E	E	E	E	E	E	E	E	E	E	E	
1	D	D	S	S	S	S	E	E	E	E	E	E	E	E	E	E	E	E	E	E	
2		DU	D	D	S	S	S	S	S	S	S	S	S	E	E	E	E	E	E	E	
3		DU	DU	DU	D	S	S	S	S	S	S	S	S	S	S	S	S	S	E	E	
4			DU	DU	DU	DU	D	S	S	S	S	S	S	S	S	S	S	S	S	S	
5				DU	DU	DU	DU	DU	D	S	S	S	S	S	S	S	S	S	S	S	
6					DU	D	S	S	S	S	S	S	S	S							
7						DU	S	S	S	S											
8							DU	S	S												
9								DU													
10									DU												
11										DU											
12											DU										
13												DU									
14													DU								
15														DU							
16															DU	DU	DU	DU	DU	DU	
17																DU	DU	DU	DU	DU	
18																	DU	DU	DU	DU	
19																		DU	DU	DU	
20																			DU	DU	
21																				DU	

In the dose determining phase of Part B, dose-de-escalation will follow a modified 3+3 design as detailed in Section 5.2.1.1.3. At the RP2D level in Part B at least 6 subjects will be enrolled. All decisions on dose de-escalation will be made by the Sponsor only after discussions between Sponsor and Investigators have occurred.

5.2.1.1.1 Dose Limiting Toxicity Criteria

The same DLT criteria will be utilized for study Part A and Part B. All toxicities will be graded using CTCAE v 4.03. The DLT window of observation will begin at the administration of the initial dose of ADXS31-142 and end 1 week following the second dose of ADXS31-142. The occurrence of any of the following toxicities will be considered a DLT, if judged by the investigator to be possibly, probably or definitely related to study treatment administration. Treatment modifications for DLT are shown in Table 8 and Table 9.

General:

1. Prolonged delay (>2 weeks) in initiating the second dose due to treatment-related toxicity
2. Missing the second dose of ADXS31-142 or pembrolizumab (MK-3475) as a result of AE(s) during the first cycle.

Hematologic:

1. Grade 4 hematologic toxicity.
2. Febrile neutropenia, defined as absolute neutrophil count (ANC) $< 1000/\text{mm}^3$ with a single temperature of >38.3 degrees C (101 degrees F) or a sustained temperature of ≥ 38 degrees C (100.4 degrees F) for more than 1 hour.
3. Grade 3 thrombocytopenia lasting >72 hours.
4. Grade 4 thrombocytopenia.

Non-Hematologic:

1. \geq Grade 3 non-hematologic toxicity, (excluding nausea, vomiting and/or diarrhea lasting <3 days and reversible with medical intervention).
2. Grade 3 non-hematologic laboratory value that does not downgrade to Grade 2 within 3 days after onset of the event despite optimal medical management (excluding transient Grade 3 laboratory value abnormalities reversible within 5 days and without medical intervention).
3. Listeremia: positive blood culture(s) along with persistent (for 72 hours post dose) symptoms consistent with listeremia (e.g., fever and muscle aches, often preceded by diarrhea or other gastrointestinal symptoms).
4. \geq Grade 3 flu-like or cytokine release symptoms that persist for >24 hours after ADXS31-142 administration despite symptomatic treatment (Refer to Section 7.2.3.2).

Subjects who experience a DLT at Dose Level -1 of 0.5×10^9 will be discontinued from study treatment. However, subjects who experience a DLT at DL 1 of 1×10^9 may be eligible to receive ADXS31-142 at a lower dose level for subsequent doses and cycles following discussion and agreement between the Investigator and Sponsor.

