If, following the rules above the dose is de-escalated, the 3 + 3 rules above will be repeated. Should additional de-escalation be required, a dose lower than 0.5×10^9 may be considered or the Sponsor may decide to take other action (e.g., stop the trial) based on a comprehensive review of the data from this trial as well as other trials.

This protocol will also allow de-escalation to an intermediate, not pre-defined and not previously-studied dose, if evaluation of toxicity at such a dose is desired in lieu of proceeding directly to the dose expansion stage of the trial.

Table 7 ADXS31-142 and Pembrolizumab (MK-3475) Combination Therapy Doses to be used in Trial Part B

Drug	Dose Level	Dose	Route of Administration	Regimen
ADXS31-142	11	1×10^9	IV infusion	Day 1 of Weeks 1, 4 and 7 of 12-week cycle
	-1	0.5×10^9	IV infusion	Day 1 of Weeks 1, 4 and 7 of 12-week cycle
Pembrolizumab (MK-3475)		200 mg	IV infusion	Day 1 Q3W of 12-week cycle

Cohort Expansion: Once the RP2D is decided, an additional cohort of subjects will be enrolled at the selected RP2D for combination therapy. The number of subjects will depend on the number of subjects previously treated in the dose-finding portion. It is planned to treat a total of approximately 30 subjects at the RP2D. Subjects will be enrolled on a rolling basis.

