	3-4 or Recurrent 2	Permanently discontinue	Permanently discontinue

Toxicity	Hold Treatment For Grade	Timing for Restarting Treatment	Discontinue Subject
Renal Failure or Nephritis	2	Toxicity resolves to Grade 0-1	Toxicity does not resolve within 12 weeks of last dose or inability to reduce corticosteroid to 10 mg or less of prednisone or equivalent per day within 12 weeks.
	3-4	Permanently discontinue	Permanently discontinue
All Other Drug-Related Toxicity ²	3 or Severe	Toxicity resolves to Grade 0-1	Toxicity does not resolve within 12 weeks of last dose or inability to reduce corticosteroid to 10 mg or less of prednisone or equivalent per day within 12 weeks.
	4	Permanently discontinue	Permanently discontinue

Note: Permanently discontinue for any severe or Grade 3 (Grade 2 for pneumonitis) drug-related AE that recurs or any life-threatening event.

¹ For subjects with liver metastasis who begin treatment with Grade 2 AST or ALT, if AST or ALT increases by greater than or equal to 50% relative to baseline and lasts for at least 1 week then subjects should be discontinued.

² Subjects with intolerable or persistent Grade 2 drug-related AE may hold study medication at physician discretion. Permanently discontinue study drug for persistent Grade 2 adverse reactions for which treatment with study drug has been held, that do not recover to Grade 0-1 within 12 weeks of the last dose.

If toxicity does not resolve to Grade 0-1 within 12 weeks after last infusion, trial treatment should be discontinued after consultation with the Sponsor. With Investigator and Sponsor agreement, subjects with a laboratory AE still at Grade 2 after 12 weeks may continue treatment in the trial only if asymptomatic and controlled. For information on the management of AEs, see [Section 5.6.1](#).

Subjects who experience a recurrence of the same severe or life-threatening (per CTCAE) event at the same grade or greater with re-challenge of pembrolizumab (MK-3475) should be discontinued from trial treatment.

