5.2.1.2.2 ADXS31-142

The most likely anticipated AEs associated with ADXS31-142 are comprised primarily of individual flu-like symptoms (e.g., fatigue, lethargy and low grade fever) or cytokine release symptoms (e.g., constitutional symptoms such as fever, chills, rigors, headache, nausea, vomiting, tachycardia, shortness of breath, hypotension, and rash). These symptoms usually present within 2-4 hours after the completion of infusion and are often mild to moderate and transient in nature or respond quickly to symptomatic treatment. In rare instances, they may last up to 24 hours. No cumulative or delayed toxicity has been observed.

Less likely AE's include increase heart rate, low blood pressure, muscle aches, headaches, allergic reaction, changes in blood chemistry, changes in blood counts, and short term changes in liver function.

Rare but serious AEs include high fever, difficulty breathing and hypotension.

██████████ ADXS31-142 has a tropism for the liver. Transient asymptomatic elevations of ALT and alkaline phosphatase were observed after dosing with ADXS11-001 in the Phase 1 trial without prophylactic medication administration. For that reason, subjects with significant liver disease are excluded, and particular attention is to be paid to hepatic abnormalities.

The dose of ADXS31-142 will not be modified (e.g., reduced or increased) unless if it is determined that the toxicities are clearly attributed to ADXS31-142 or the combination, the treatment modification guidelines for drug-related AEs in [Table 9](#) shown below are to be followed.

Table 9 Treatment Delay/Discontinuation Guidelines for Drug-Related Adverse Events-ADXS31-142

Toxicity	Grade	Hold treatment	Timing for restarting treatment	Discontinue treatment
Hematologic	1-3	No	N/A	N/A
	4	Yes	Toxicity resolves to ≤Grade 1 or baseline	Toxicity does not resolve to ≤Grade 1 or baseline within 12 weeks
Non-hematologic, excluding cytokine release symptoms and DLTs	1	No	N/A	N/A
	2-3	Yes	Toxicity resolves to ≤Grade 1	Toxicity not resolved to ≤Grade 1 within 12 weeks of last infusion ^a
	4	N/A	Permanently discontinue treatment	Permanently discontinue treatment

^a With Investigator and Sponsor agreement, subjects with a non-heme AE (e.g., alopecia, neuropathy) still at grade 2 after 12 weeks, may continue treatment if only asymptomatic and controlled.

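### In Part B the DLT window can close while the second pembrolizumab dose is still on hold, so the same subject may or may not count as a DLT

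*Combined protocol and SAP*

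**What the plan says.** Section 5.2.1.1.1 applies one set of DLT criteria to Parts A and B and ties the window to ADXS31-142 only: "The DLT window of observation will begin at the administration of the initial dose of ADXS31-142", and it must "end 1 week following the second dose of ADXS31-142".

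Two General criteria concern the second dose:

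- Criterion 1: "Prolonged delay (>2 weeks) in initiating the second dose due to treatment-related toxicity". No drug is named.
- Criterion 2: "Missing the second dose of ADXS31-142 or pembrolizumab (MK-3475) as a result of AE(s) during the first cycle". Both drugs are named, but no date is given by which a held dose becomes a missed one.

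Table 7 (Section 5.2.1.1.3) schedules ADXS31-142 on "Day 1 of Weeks 1, 4 and 7 of 12-week cycle" and pembrolizumab on "Day 1 Q3W of 12-week cycle", so both second doses are due on the same day.

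Holds follow separate tables. Table 8 governs pembrolizumab, and the text below it says "If toxicity does not resolve to Grade 0-1 within 12 weeks after last infusion, trial treatment should be discontinued". Section 5.2.1.2.2 brings Table 9 into play for ADXS31-142 "if it is determined that the toxicities are clearly attributed to ADXS31-142 or the combination". One drug can therefore be given while the other is held.

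Section 5.2.1.1.3 uses the DLT count in a modified 3+3 rule. Dose Level 1 is accepted with at most 2 DLTs in 6 subjects and abandoned with 2 or more in the first 3, or with 3 or more in 6.

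**The concern.** The window follows one drug, while criterion 2 expressly covers the other drug and carries its own, longer period. When pembrolizumab alone is on hold, the window runs out before the plan can say whether the second dose was delayed too long or missed. By the window, the subject has no DLT. By criterion 2, the subject may have one. Nothing in Section 5.2.1.1.1 says which governs, or whether such a DLT is dated by the onset of the adverse event or by the delay or omission of the dose.

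Part B has to establish the RP2D of the combination from as few as six subjects, and one subject can change the decision: 2 of 6 is accepted and 3 of 6 is not. If the window is applied literally, the error goes one way, towards accepting the dose.

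**Working it through.** The plan gives no operating characteristics for the Part B rule and no inferential analysis, so there is no figure of its own to reproduce.

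**1. Calendar.** Take the first dose as Day 1. Day 1 of Week w is then 7(w − 1) + 1.

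- ADXS31-142 (Table 7): Days 1, 22 and 43.
- Pembrolizumab (Table 7, every 3 weeks): Days 1, 22, 43 and 64.
- Window end: second ADXS31-142 dose + 7 days, so 22 + 7 = Day 29 on schedule.
- Pembrolizumab delay of more than 14 days: first true on 22 + 15 = Day 37.
- End of the first cycle: 12 × 7 = Day 84.
- Limit of a pembrolizumab hold, 12 weeks after an infusion on Day 1: 1 + 84 = Day 85.

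**2. Does the delay mature inside the window?** Section 5.2.2 allows 7 days either side for Day 1 of each cycle, and the per-infusion window in the flow chart is blacked out. The 7-day shifts below are therefore a sensitivity check only.

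| Second ADXS31-142 dose given | Window closes | Pembrolizumab delay >2 weeks first true | Result |
|---|---|---|---|
| Day 15 (7 days early) | Day 22 | Day 37 | 15 days too late |
| Day 22 (on schedule) | Day 29 | Day 37 | 8 days too late |
| Day 29 (7 days late) | Day 36 | Day 37 | 1 day too late |
| Day 30 (8 days late) | Day 37 | Day 37 | inside |

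The delay falls inside the window only if ADXS31-142 is itself at least 8 days late.

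**3. Does a missed dose fall inside the window?** The due date, Day 22, is never after closure in the table. On schedule, an omission or permanent discontinuation decided by Day 29 is visible. A dose still on hold at Day 29 is different, because its status depends on the undefined cut-off. If a dose is missed once the next three-weekly date arrives, that is Day 43, which is 43 − 29 = 14 days after closure. If it is judged over the whole first cycle, that is Day 84, which is 84 − 29 = 55 days after closure.

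**4. Who is exposed?** Most non-hematologic toxicity of Grade 3 or higher is a DLT anyway. Table 8 also holds pembrolizumab for Grade 2 events such as colitis, pneumonitis and hypophysitis. Generally these reach DLT status only through General criteria 1 or 2. If such an event is attributed to pembrolizumab alone, Table 9 does not hold ADXS31-142. Section 5.6.1 describes steroid tapers of at least four weeks for these events, which makes a prolonged course plausible. It does not prove a long hold, because the restart column of Table 8 refers to grade only.

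**5. Effect on the 3+3 decision (illustration).** With DLT probability p, independent between subjects, the rule in Section 5.2.1.1.3 accepts Dose Level 1 with probability

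A(p) = (1 − p)³(1 − p³) + 3p(1 − p)²[(1 − p)³ + 3p(1 − p)²].

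- A(0.20) = 0.512 × 0.992 + 0.384 × 0.896 = 0.852
- A(0.30) = 0.343 × 0.973 + 0.441 × 0.784 = 0.679
- A(0.40) = 0.216 × 0.936 + 0.432 × 0.648 = 0.482

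The documents give no rate of pembrolizumab-only holds. The losses below are assumptions, and they suppose that every such event goes uncounted.

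| True DLT rate | All counted | 5 points lost | 10 points lost | 15 points lost |
|---|---|---|---|---|
| 30% | 0.679 | 0.771 | 0.852 | 0.917 |
| 40% | 0.482 | 0.581 | 0.679 | 0.771 |

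**The case against.** A reader might infer more than the documents support, in three ways.

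- *A missed second pembrolizumab dose can never be recorded inside the window.* This is wrong. The dose is due on Day 22, and Table 8 requires permanent discontinuation for several toxicities, so a miss can be final by Day 29.
- *Criterion 1 certainly covers pembrolizumab.* It names no drug and is shared with monotherapy. If it means ADXS31-142 only, it raises no conflict, because a late ADXS31-142 dose moves the window with it.
- *The affected subject is scored DLT-free.* The documents do not say this. It is what the window gives if read literally. Criterion 2 can be read as setting its own period, and the causal event may well have begun inside the window.

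The affected group is also small. Section 7.1.3.1 requires laboratory results to meet Table 3 before each dose, so hepatic or renal values outside those limits stop ADXS31-142 too and move the window. Table 9 holds ADXS31-142 for Grade 2–3 non-hematologic events attributed to it or to the combination. Finally, de-escalation may rest on interim safety review as well as DLTs, after discussion between Sponsor and investigators. No section fixes the decision at Day 29, and acceptance always needs a second group of three, by which time a late result in the first three may be known.

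All of this stands as a limit on scope and size. It does not remove the conflict. A discretionary review does not settle whether a held subject counts towards 2 or 3 of 6, and a late result in the last three subjects can still arrive after the count is taken.

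**Conclusion.** The point holds in a limited form. For a subject given ADXS31-142 on time whose pembrolizumab alone is on hold when the window closes, the stated window ends before the stated criteria can be resolved. The gap is 8 days for a delay of more than two weeks, if criterion 1 covers pembrolizumab. For a miss not yet declared it is 14 days or more, if the cut-off is the next scheduled dose or later. Two sites could classify the same subject differently.

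The day counts assume dosing on the nominal schedule. The effect on acceptance is illustrative: 68% to 85% if a true rate of 30% is counted as 20%, and less if fewer events are lost. The 3+3 arithmetic is exact, but the size of the loss is assumed, and the narrowness of the group suggests that it could be small. The direction is clear under the literal window reading: towards accepting the dose.

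**What to change.** In Section 5.2.1.1.1, with a cross-reference in Section 5.2.1.1.3, reconcile the window with General criteria 1 and 2:

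- State which drug's second dose criterion 1 covers.
- State when a held second dose counts as missed.
- Align the first-cycle wording of criterion 2 with the window.
- Attribute a DLT under these two criteria by onset of the causal, related adverse event inside the window, whenever the delay or omission is established.
- If a covered second dose is still on hold when the window closes, keep that subject's DLT status pending until the dose is given or the stated cut-off passes, and take no 3+3 acceptance decision until then.

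This changes how DLTs are counted, not how either drug is dosed or held. The cost is a few sentences, and an affected cohort may wait about one to two weeks longer (8 days to Day 37, 14 days to Day 43). A cohort with no such hold is not delayed.
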